CANPAIN feasibility study: evaluating the feasibility of subsequently undertaking a pragmatic real world trial investigating CBMP in chronic pain patients

(SHORT) CANPAIN Feasibility study

Chief Investigator:

[name]
Clinical Lead of Harley Street (CPC) limited

Sponsored by:

Harley Street (CPC) Limited
Trading as LVL Health

Protocol version number and date:

CANPAIN feasibility v2 16 02 2022

PROTOCOL VERSIONS

Version Stage	Versions No	Version Date	Protocol updated & finalised by;	Appendix No detail the reason(s) for the protocol update
Current	2	16 02 22	NA	NA
Previous	1	17 08 22	NA	NA

SIGNATURES AND AGREEMENT WITH PROTOCOL

Trial title: CANPAIN feasibility study: evaluating the feasibility of subsequently undertaking a pragmatic real world trial investigating CBMP in chronic pain patients

We, the undersigned, agree to conduct this trial according to this Trial Protocol. We agree that the trial will be carried out in accordance with Good Clinical Practice (GCP), with the Declaration of Helsinki (with amendments) and with the laws and regulations of the countries in which the trial takes place.

On behalf of the Chief Investigator:

Signature:  **Date. 16/Feb/2022**

Print Name(in full):.....[name].....

Position:.....Chief Investigator.....

On behalf of the Study Sponsor:

Signature:  **Date. 16./Feb./2022**

Print Name(in full): [name]

Position:..... Director

STUDY SUMMARY

Identifiers	
IRAS Number	304548
REC Reference No	TBD
Sponsor Reference No	CANPAIN feasibility 1
Other research reference number(s) (if applicable)	
Full (Scientific) title	
Health condition(s) or problem(s) studied	Non-cancer chronic pain
Study Type i.e. Cohort etc	Feasibility study
Target sample size	Number collected over a 3 month period but with a minimum target of 100 subjects
STUDY TIMELINES	
Study Duration/length	3 months
Expected Start Date	1 st March 2022
End of Study definition and anticipated date	Last patient last visit (2 nd June 2022)
FUNDING & Other	
Funding	Study will be funded by the Sponsor
Other support	NA
KEY STUDY CONTACTS	Study Site: [name] Email: [contact] [contact] Full contact details including phone, email and fax numbers
Chief Investigator	[name]

KEY ROLES AND RESPONSIBILITIES

SPONSOR: The Sponsor is responsible for ensuring before a study begins that arrangements are in place for the researchers to deliver the research as proposed and allocate responsibilities for the management, monitoring and reporting of the research.

1 INTRODUCTION

The below proposed study will recruit existing patients of the private clinic who have already consented to and agreed to receive and self-fund the cannabis-based medicinal product offered by the clinic.

The CANPAIN study has been devised to evaluate the efficacy and safety of a defined cannabis based medicinal product (CBMP) delivered by inhalation to patients with chronic pain attending a private clinic. Prior to commencing the CANPAIN study, and as suggested by the Oxford A REC, we propose to conduct a feasibility study. This study will aid in establishing likely rates of patient recruitment, duration of participant enrolment in the study, the demographic and geographic spread of patients, patient acceptability of data collection and identify any issues with technological and drug delivery logistics.

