2 BACKGROUND AND RATIONALE

The CANPAIN protocol has been submitted previously to the Oxford A REC for ethical review (see Appendix 1), but a non-acceptance opinion was received. It was recommended that a feasibility study be considered to address concerns regarding recruitment rates and acceptability of the study. The feasibility study will be based within a private clinic setting and will only involve existing patients of the clinic. The treatment regime, tests that the patients are required to take, the clinical information they are required to provide, and the informed consent required for treatment, will all follow the clinical protocol in Appendix 1. We wish to assess the feasibility of conducting the study within the private clinic to aid a future submission to Oxford A REC of the CANPAIN study. This subsequent application will aim to address the Oxford A REC concerns around the control group.

Patient Clinical Pathway

This section provides an overview of the clinical pathway patients at the clinic will follow from initial assessment through to provision of CBMP and vaporiser device.

Prior to receiving the clinical service, the prospective patient's application and medical information will be assessed by a multi-disciplinary team to determine if they are suitable for CBMP treatment. This assessment will utilise the inclusion and exclusion criteria outlined below as well as the clinicians' experience and will comply with NHS England and GMC guidance on prescribing both CBMP and unlicensed medications.

If the patient meets the requirements for CBMP treatment, they will sign a consent form for undertaking certain screening tests. Once consent has been gained patients will be sent a urine pregnancy test (if applicable), a urine cannabis test to establish existing cannabis use and a saliva genetic test to subsequently determine if genetic markers can determine sensitivity to cannabis. If the patient is pregnant, they will not be able to attend the clinic. If they fail the cannabis test, they will have to stop use for 3 weeks and provide a negative urine test before they can commence treatment at the clinic.

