3 OBJECTIVES

3.1 Primary Objective

Domain 1

- 1) Assess rate of recruitment to the clinic.
- 2) Assess the number/proportion of patients that cease treatment at the Clinic.
- 3) Assess the number of patients that complete all questionnaires required.
- 4) Assess the number of patients that experience safety issues.

Domain 2

- 1) Assess the timeliness and efficiency of CBMP delivery to the patient.
- 2) Assess the presence of issues with the usability of the inhalation device.

Domain 3

- 1) Assess the study acceptability via answers to comment forms:
 - a. ease of onboarding.
 - b. ease of answering questionnaires.
 - c. evidence of questionnaire fatigue.
 - d. satisfaction of service.

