4 CONSENT

Informed consent will be obtained from participants when onboarding to the clinical service for treatment with a CBMP. If they subsequently decide to join the feasibility study, then they will sign a separate consent form for the study.

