5 ELIGIBILITY CRITERIA

5.1 Inclusion Criteria

1. A consented patient at the clinic;
2. Male or female 18-85 years old;
3. Diagnosed with chronic non-cancer pain;
4. Is currently receiving standard of care but still has pain, has completed standard of care pain treatment, does not want standard of care treatment, or standard of care is contraindicated. An inadequate response is defined as the subject receiving standard analgesic agents and still has pain, has unpleasant side effects or wishes to reduce their intake of standard of care analgesic agents, e.g. a subject receiving opioids who wishes to dose reduce in light of the “opioid crisis”;
5. Despite being on or having received standard of care and has still pain (>3 on the Pain NRS); and
6. Signed and dated consent form from the patient.

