7.2 Exclusion Criteria

1. Pregnant or lactating females or females who are planning a pregnancy during the study;
2. Positive pregnancy test at time of joining the clinic;
3. Major organ failure, renal, lung or liver failure;
4. Participants having active liver disease or unexplained persistent elevation of serum transaminases > 3 times the upper limit of normal;
5. Participants with a creatinine clearance < 60mL/min;
6. History of cardiac or respiratory failure;
7. History of recent myocardial infarction or poorly controlled ischaemic heart disease;
8. Severe respiratory disease (e.g., GOLD 3 for COPD or asthmatics requiring high doses of oral corticosteroids);
9. History or presence of alcohol or substance abuse, including analgesics used as standard of care;
10. Participation in a clinical trial of an investigational medicinal product;
11. With any known or suspected history or family history of schizophrenia, or other psychotic illness; history of severe personality disorder or other significant psychiatric disorder disorders other than depression associated with their underlying condition;
12. Known hypersensitivity to cannabis or allergy to cannabis or CBMP; and
13. Currently taking cannabis and does not agree to a 3 week wash out period.

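### Already-treated patients can be pooled with new starters, and those who left before study consent are not counted, so cessation, safety, completion and onboarding results may look too favourable

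*Protocol*

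**What the plan says.** Section 1 of the feasibility protocol states that the study "will recruit existing patients of the private clinic who have already consented to and agreed to receive and self-fund the cannabis-based medicinal product". Section 2 repeats the restriction: the study "will only involve existing patients of the clinic". Section 4 places treatment consent at onboarding and study consent afterwards: "If they subsequently decide to join the feasibility study, then they will sign a separate consent form for the study". The interval between the two is not fixed. On treatment status, section 5.1 requires only "A consented patient at the clinic".

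The primary objectives in section 3.1 include "Assess the number/proportion of patients that cease treatment at the Clinic" and "Assess the number of patients that experience safety issues", together with the number completing all questionnaires and comment-form answers on ease of onboarding. Neither a starting point for observation nor a denominator is given. The clinical pathway in section 2 adds that patients who do not complete the required questionnaires may not go on using the medication.

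The CANPAIN protocol in Appendix 1 describes its own entry in two ways. Section 6.1 sets Day 0 at the first prescription. Figure 1, Stage 4 has patients invited during the clinic treatment phase and followed from then on. It also describes CBMP as free (section 6.1) and as self-funded (section 6.5.3).

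**The concern.** A cessation proportion depends on when observation begins. If some participants are weeks or months into treatment when they consent to the study, the early part of their treatment has already acted as a filter. Patients who stopped during it are no longer existing patients to be recruited, and those who remain are counted alongside people just starting. The same holds for safety issues at first use and around the dose step one month after baseline (Appendix 1, section 6.5.1). It holds for questionnaire completion too, because non-completers lose access to treatment. People who gave up before becoming clinic patients cannot rate onboarding.

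This differs from unequal follow-up within the shared three-month window: it would remain if every participant were observed for the same time. The feasibility study is meant to inform a resubmission of CANPAIN, including how long participants stay enrolled (sections 1 and 2). A pooled figure of unknown composition is a weak basis for that.

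**Working it through.** **Can treated patients enter?**

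- Sections 1 and 2 restrict the study to existing patients who have consented to treatment.
- In the section 2 pathway, the patient signs treatment consent at the consultation, the doctor then prescribes, and the device and medicine are couriered. A consented patient is therefore at or near first prescription, or some way past it.
- Section 5.1 does not require patients to be untreated or newly prescribed.
- One exclusion reads "Positive pregnancy test at time of joining the clinic", which treats joining the clinic as an event distinct from joining the study.

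Treated patients can enter. The documents do not say how many will.

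**Who is missing?** Anyone who stopped treatment before study consent, and anyone who abandoned onboarding before treatment consent. The second loss needs no assumed rate, because such people fail the first inclusion criterion. Section 3.2 counts webpage enquiries and registration forms, but not losses between registration and first prescription.

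**How large could the effect be?** The protocol states no figure to reproduce: the minimum of 100 has no calculation behind it, and no stopping rates are given. The following is an illustration on assumed rates.

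Let m1 be the probability of stopping in month 1 and m2 the monthly probability afterwards. Everyone is followed for three months.

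- New starters: 1 − (1 − m1)(1 − m2)²
- Patients already past month 1: 1 − (1 − m2)³

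With m2 = 5%, the second expression is 1 − 0.95³ = 14.3%.

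| m1 | m2 | New starters | Already past month 1 | Half and half |
|---|---|---|---|---|
| 5% | 5% | 14.3% | 14.3% | 14.3% |
| 10% | 5% | 1 − 0.90 × 0.95² = 18.8% | 14.3% | 16.5% |
| 15% | 5% | 1 − 0.85 × 0.95² = 23.3% | 14.3% | 18.8% |
| 20% | 5% | 1 − 0.80 × 0.95² = 27.8% | 14.3% | 21.0% |
| 5% | 10% | 1 − 0.95 × 0.90² = 23.1% | 1 − 0.90³ = 27.1% | 25.1% |

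For month-1 stopping of 10-20%, the shortfall against new starters is 4.5 to 13.5 points if everyone is already past month 1, and 2.3 to 6.8 points in a half-and-half sample. It is zero when the rates are equal, and the sign changes when stopping rises later.

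**Funding.** Suppose feasibility patients pay, CANPAIN patients do not, and cost causes an extra stopping probability x each month in the feasibility study only. With m1 = 20% and m2 = 5%, free-supply starters show 27.8%. Self-funding patients past month 1 show 1 − (0.95 × (1 − x))³, which is 26.5% at x = 5% and 33.2% at x = 8%. Cost could offset or reverse the difference.

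**Precision.** At n = 100 the 95% half-width, 1.96 × √(p(1 − p)/100), is 5.9 points at p = 10% and 9.0 points at p = 30%.

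**The case against.** *Existing need not mean treated.* Patients may have agreed to CBMP without having started it, and recruitment to the clinic is itself an outcome, which suggests that new arrivals are observed. The exclusion "Currently taking cannabis and does not agree to a 3 week wash out period" sits awkwardly with patients already on the clinic's product. This stands in part: a reader might infer that all participants are on treatment, and the documents do not say so. But section 2 makes the three-week stop a condition for starting clinic treatment, and nothing extends it to the clinic's own CBMP. A mixture remains possible, with no provision to separate it.

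*CANPAIN may have the same selection.* This is the strongest objection. A reader might infer that CANPAIN enrols only starters, but the documents do not settle it: section 6.1 of Appendix 1 points to first prescription and Figure 1 to patients under treatment. If Figure 1 governs, a sample of treated patients resembles its target. The objection removes any blanket instruction to plan from new starters alone, but it does not justify the pooled figure, which matches neither entry point.

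*Direction and size.* No stopping rates are given, the dose step comes at one month so intolerance need not cluster before it, and self-funding could push cessation up. All of this stands. The half-and-half shortfall is also of the same order as, or smaller than, the sampling error at 100 patients. Bias and sampling error are different problems, though, and more patients would not cure the first.

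*Losses are partly visible.* Enquiry and registration counts exist, and the health record may hold earlier events for those who join. Neither recovers patients who stopped before study consent or who were lost between registration and first prescription.

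*This belongs in an analysis plan.* Who may enter, and when, is fixed in the protocol. Analysing participants alone cannot restore people who never became participants.

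**Conclusion.** The point holds in a limited form. The entry rules allow already-treated patients to be pooled with new starters and leave out those who stopped or gave up before study consent. Cessation, safety, completion and onboarding results may therefore look better than they would from first prescription.

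That they *will* look better is a stronger reading that the documents do not support. It requires early stopping or early intolerance to exceed later levels. Under the assumed 10-20% in month 1 and 5% a month afterwards, the contrast is 19-28% against 14% over three months. Only the selection of onboarding raters is independent of assumed rates.

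The change is worth making because it is cheap and removes the mixing whichever way CANPAIN entry is resolved. Without the first-prescription date, nobody could tell afterwards which row of the table applied.

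**What to change.** 1. Take the first-prescription date for each participant from the electronic health record, which section 6 already uses as the data source.
2. Report cessation, safety issues and questionnaire completion by time since first prescription, separately for patients who start CBMP after study consent and for those already on it. Treat the latter as delayed entries, at risk only from study consent.
3. Next to the onboarding comments, give the aggregate clinic count of patients who registered or began onboarding but never started, extending the enquiry and registration counts in section 3.2.
4. In Appendix 1, reconcile section 6.1 with Figure 1, Stage 4 on the entry point, and section 6.1 with section 6.5.3 on who pays. Plan CANPAIN from the group that matches the entry point finally stated.

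The cost is one extra date, a split table and an aggregate count. Each group is smaller than the full sample: if 100 patients divided evenly, the half-widths of 5.9 and 9.0 points would grow by √2, to about 8.3 and 12.7 points.

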2 BACKGROUND AND RATIONALE

The CANPAIN protocol has been submitted previously to the Oxford A REC for ethical review (see Appendix 1), but a non-acceptance opinion was received. It was recommended that a feasibility study be considered to address concerns regarding recruitment rates and acceptability of the study. The feasibility study will be based within a private clinic setting and will only involve existing patients of the clinic. The treatment regime, tests that the patients are required to take, the clinical information they are required to provide, and the informed consent required for treatment, will all follow the clinical protocol in Appendix 1. We wish to assess the feasibility of conducting the study within the private clinic to aid a future submission to Oxford A REC of the CANPAIN study. This subsequent application will aim to address the Oxford A REC concerns around the control group.

Patient Clinical Pathway

This section provides an overview of the clinical pathway patients at the clinic will follow from initial assessment through to provision of CBMP and vaporiser device.

Prior to receiving the clinical service, the prospective patient's application and medical information will be assessed by a multi-disciplinary team to determine if they are suitable for CBMP treatment. This assessment will utilise the inclusion and exclusion criteria outlined below as well as the clinicians' experience and will comply with NHS England and GMC guidance on prescribing both CBMP and unlicensed medications.

If the patient meets the requirements for CBMP treatment, they will sign a consent form for undertaking certain screening tests. Once consent has been gained patients will be sent a urine pregnancy test (if applicable), a urine cannabis test to establish existing cannabis use and a saliva genetic test to subsequently determine if genetic markers can determine sensitivity to cannabis. If the patient is pregnant, they will not be able to attend the clinic. If they fail the cannabis test, they will have to stop use for 3 weeks and provide a negative urine test before they can commence treatment at the clinic.

The patient will then book a consultation at the clinic. They will review the treatment consent prior to the consultation and will be explained the treatment and safety consideration by the specialist doctor at the clinic and if they are in agreement to receive the unlicensed medicines, they will sign the consent form in front of the doctor. The doctor will then prescribe the medication using his private controlled drug PIN on a FP10PCD form and send this to the pharmacy. The inhalation device with instructions and the medicines will be couriered to the patient using controlled drug procedures. The patient will need to fill out baseline pain and quality of life questionnaires to ascertain their base level before taking the medicines for the first time. After each inhalation session the patient must fill in safety questions, which are reviewed by the clinic, before they can use the medication again. The

patient has to fill out pain questionnaires once a week and a quality-of-life questionnaire once a quarter. If they do not do so they cannot continue using their medication. The patients will also be asked to fill out a questionnaire on quality of the service and any complaints they have.

The feasibility study will be conducted over a 3-month period with a minimum target recruitment number of 100 patients. Feasibility will be assessed through 3 distinct domains: Recruitment and patient experience, medication logistics and data management.

Patient experiences (part of domain 3) will be captured using comment forms, requesting feedback on ease of onboarding, ease of answering questionnaires, evidence of questionnaire fatigue and their satisfaction of service.

3 OBJECTIVES

3.1 Primary Objective

Domain 1

- 1) Assess rate of recruitment to the clinic.
- 2) Assess the number/proportion of patients that cease treatment at the Clinic.
- 3) Assess the number of patients that complete all questionnaires required.
- 4) Assess the number of patients that experience safety issues.

Domain 2

- 1) Assess the timeliness and efficiency of CBMP delivery to the patient.
- 2) Assess the presence of issues with the usability of the inhalation device.

Domain 3

- 1) Assess the study acceptability via answers to comment forms:
 - a. ease of onboarding.
 - b. ease of answering questionnaires.
 - c. evidence of questionnaire fatigue.
 - d. satisfaction of service.

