6 DATA HANDLING AND MANAGEMENT

Information related to feasibility study will be extracted from the participating clinical sites electronic health record (EHR) system which will contain all the relevant patient information, prescribing information, safety information and questionnaires completed. At the end of the feasibility study information on the relevant domains will be extracted and collated into a feasibility study report.

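### Questionnaire fatigue is read only from a further, unenforced comment form and is not linked to the completion and cessation counts, so it may be understated

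*Protocol*

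**What the plan says.** Protocol section 3.1 makes acceptability part of the primary objective. Domain 3 is worded "Assess the study acceptability via answers to comment forms", and its third item is "evidence of questionnaire fatigue". Section 2 names the same instrument: patient experiences "will be captured using comment forms, requesting feedback on ease of onboarding, ease of answering questionnaires, evidence of questionnaire fatigue" and satisfaction. Neither place names another source for the fatigue item.

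Two items in Domain 1 of the same primary objective bear on the matter. Item 2 is "Assess the number/proportion of patients that cease treatment at the Clinic" and item 3 is "Assess the number of patients that complete all questionnaires required". Section 6 draws the feasibility data from the electronic health record, whose contents include "prescribing information, safety information and questionnaires completed".

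Section 2 also sets out what happens when questionnaires go unanswered. Safety questions must be answered and reviewed after each inhalation session before the next one. For the weekly pain and quarterly quality-of-life questionnaires it says "If they do not do so they cannot continue using their medication". No such consequence is attached to the comment form.

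**The concern.** The item asks whether patients have grown tired of forms, and the only named way to find out is one more form. A patient worn down by questionnaires, or who has left because of them, may well be less willing to return it, and nothing in the protocol obliges them to. Non-return is then related to the thing being measured, and the returned forms over-represent patients who coped.

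This matters because section 2 says the ethics committee recommended a feasibility study to settle its doubts about recruitment rates and the acceptability of the study, and section 1 lists patients' acceptance of the data collection among the aims. An answer that leans towards patients who tolerated the questionnaires would be weak support when the main study is resubmitted.

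**Working it through.** The protocol gives no expected level of fatigue, no return rate for the form and no precision target, so it has no figure to reproduce. The check has two parts: what the text ties to the fatigue item, and how far selective return could move the result.

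**1. What each source can show**

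- *Comment form (Domain 3).* It is the only source tied to fatigue. The text does not say whether patients who stop treatment are offered it.
- *Full completion (Domain 1, item 3).* Non-completers follow by subtraction from the number enrolled. It is an all-or-nothing count, so it shows no decline over the 3 months. Because medication depends on answering, a tired patient may keep answering and count as a completer.
- *Cessation (Domain 1, item 2).* As worded, it counts patients who stop without giving reasons. A patient who left because of the questionnaires looks the same as one who left for any other reason.
- *Health record (section 6).* It holds the questionnaires completed. The protocol does not say that prompt or entry times are stored.

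The three sources complement one another, but the protocol does not say that the Domain 1 counts are to be read as evidence on fatigue.

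**2. Effect of selective return (all rates assumed)**

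Let f be true fatigue, and let rf and rn be the return rates of fatigued and other patients. Then

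observed fatigue among returners = f·rf / [f·rf + (1 − f)·rn].

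Take f = 30% and the minimum target of 100 patients, so 30 are fatigued and 70 are not.

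| rf | rn | Fatigued forms | Other forms | Observed |
|---|---|---|---|---|
| 90% | 90% | 27 | 63 | 27/90 = 30.0% |
| 70% | 90% | 21 | 63 | 21/84 = 25.0% |
| 50% | 90% | 15 | 63 | 15/78 = 19.2% |
| 30% | 90% | 9 | 63 | 9/72 = 12.5% |
| 90% | 70% | 27 | 49 | 27/76 = 35.5% |

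The first row shows no bias when the return rates are equal. The last row shows overstatement when fatigued patients return more often, for example in order to complain. With returns of 50% against 90%, a true 20% would appear as 12.2% and a true 40% as 27.0%.

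**3. Bounds that need no assumption about who returns**

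Let p be observed fatigue and R the overall return rate. True fatigue lies between p·R and p·R + (1 − R). For p = 10%:

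- R = 90%: 9% to 19%
- R = 80%: 8% to 28%
- R = 70%: 7% to 37%
- R = 50%: 5% to 55%

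**4. What reporting over all consented patients would show**

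In the 50% against 90% case, the full report is 15% fatigued, 63% not fatigued and 22% not returned. The bounds are 15% to 15% + 22% = 37%, which contain the true 30%. The figure of 19.2% among returners conceals this.

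**The case against.** The strongest reply is that the behavioural evidence is already in the primary objective. Domain 1 counts full completion and cessation from a record that holds the completed questionnaires, so patients who stop answering will appear in the feasibility report. This stands. A reader might infer that such patients are invisible, or that the completion data go unused. The documents do not support either. What remains is that the counts are not connected to the fatigue item and, for the reasons in the working, cannot stand in for it alone.

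A reader might also infer that patients who stop cannot be scored on fatigue, and that fatigue is therefore certainly understated. Neither follows. The form is separate from the clinical questionnaires, and nothing bars a patient who has stopped from returning it. Understatement requires lower return among fatigued patients, and a comment form may equally attract the dissatisfied.

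Two further replies have weight. The handling of unreturned forms is commonly left to an analysis plan, so the lack of a rule here is not itself a fault. The point rests on the protocol's own choice of a single source. Also, the protocol presents the form as patient feedback and never promises a prevalence estimate; fatigue is one of four items in one of three domains, and no decision threshold hangs on it. That limits the consequence, but any summary of the forms would still be open to the same selection.

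Finally, completion records are an imperfect measure, because answering is a condition of medication. Self-report is a sensible way to find the patient who is tired but keeps answering. This is a reason to keep the form and add to it, not to replace it.

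**Conclusion.** The concern holds in a limited form. The fatigue item relies on a further form whose return is not enforced, and it is not linked to the Domain 1 counts of completion and cessation. Fatigue may be understated if fatigued patients return the form less often. Neither the direction nor the size can be established from the protocol, since every return rate used here is an assumption. On those assumptions, a true 30% could appear anywhere from 12.5% to 35.5% across the table. The reading that patients who stop are lost to the study and that fatigue is necessarily understated goes further than the documents allow. This is a worthwhile, inexpensive improvement to a primary-objective item, not a flaw that undermines the feasibility study.

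**What to change.** - Keep the comment form, and offer it also when a patient stops treatment.
- Report its answers over all consented patients, with non-return as its own category, split by Domain 1 status (completed all required questionnaires or not; ceased treatment or not).
- Add a second indicator of fatigue to Domain 3: completion of the required questionnaires by week since enrolment, from the health record. Use delay to completion only if entry times prove to be stored.
- State beside that indicator that medication depends on answering, so high completion alone does not rule out fatigue.

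The cost is a change of protocol wording, one extra occasion for offering the form, and slightly more extraction and analysis. No new visits are needed.
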